6.2. Analysis

Findings will be then classified using LUNG-RADS[1] schema and ROC analysis will be applied. Inter-observer variability will be analysed with Krippendorff's Alpha.

6.3. End of study

End of study befalls when all of the next criteria have been satisfied:

1. One year after start-up
2. At least 80% of the subjects enrolled in SOS trial have been contacted
3. The database has been fully cleaned and frozen for the analysis

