3.2. Exclusion criteria

[figure not shown]
Exclusion criteria:

- pregnancy

4. Trial Design

During this study, about 1700 subjects, who have been enrolled in SOS Observational Study will undergo a DTS. The study will be presented as an observational clinical trial and registered on clinicaltrials.gov. Initially, all the subjects that participated in the SOS study, will be contacted by phone and invited to perform a DTS in Carle Hospital. When accessing the hospital the subjects will be asked to fill-in a form to confirm that the inclusion criteria of the SOS study are still met. DTS will be then performed and blindly evaluated by two radiologists. DTS findings will be classified based on their dimension (large axis measurement), radiological characteristics (calcific, pleural, solid, partially solid and ground glass opacity) and position (in the 5 lobes). Findings will be then classified using LUNG-RADS[1] schema and ROC analysis will be applied. Inter-observer variability will be analyzed with Krippendorff's Alpha[17].

Discordant and positive cases will be discussed in a consensus session among radiologists and thoracic surgeons. The consensus results will be used in the following analysis. The subjects with one or more nodules larger than 5 mm, not clearly benign, will undergo diagnostic contrast enhanced CT and will be followed in line with Fleischner Society[2].

5. Evaluation criteria

Lung cancer will be histologically proven, following the procedure of Pathology Division that use a double blinded analysis of biological material.

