6.1. Statistical design

6.1.1. Sample size

The primary objective of this study is to calculate the detection rate on lung cancer at 5 years distance from the previous DTS. In the SOS study 1843 subjects were enrolled and lung cancer was found in 18 (0.8%) of them at baseline. 1703 subjects performed the first round DTS at one-year distance and lung cancer was found in 5 (0.3%) of them.

Assuming a binomial model for the occurrence of the disease (Flanders WD and Kleinbaum DG. Basic Models for Disease Occurrence in Epidemiology, International Journal of Epidemiology, Volume 24, Issue 1, 1 February 1995, Pages 1–7) the number of patients needed to be confident that the disease will be detected if present at or above the specified annual incidence of 0.3% with a confidence of 5% (i.e. that assuming the true incidence is at least 0.3%, then a sample consisting only of subjects without lung cancer would occur 5% of the time or less given a sample with the calculated size) is 998. Allowing for a drop out of no more than 50%, a minimum number of 1496 subjects is required.

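### The end-of-study rule permits closure at 1475 contacts, 21 below the plan's own minimum of 1496, and counts contacts although the 5% assurance depends on 998 completed examinations

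*Combined protocol and SAP*

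**What the plan says.** Section 6.3 sets three joint conditions: "End of study befalls when all of the next criteria have been satisfied". The first is "One year after start-up", the second is "At least 80% of the subjects enrolled in SOS trial have been contacted", and the third is a cleaned and frozen database. Only the second involves a number of people.

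Section 6.1.1 gives the base for that percentage, "In the SOS study 1843 subjects were enrolled", and the size target, "a minimum number of 1496 subjects is required". The target starts from 998 subjects, the number at which a sample with no lung cancer would arise at most 5% of the time if the true rate is at least 0.3%. It is then raised for a drop-out of up to 50%.

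Section 4 (Trial Design) says that "all the subjects that participated in the SOS study, will be contacted by phone and invited to perform a DTS", and expects about 1700 to have the examination. It also has attendees confirm on arrival that they still meet the inclusion criteria. The Synopsis (Overall Study design) says that those who decline the examination are interviewed by phone instead. The Synopsis (Population) restricts the study to SOS subjects without confirmed lung cancer.

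**The concern.** Three statements about how many people the study needs do not fit together. Section 4 commits to contacting everyone, Section 6.1.1 names a minimum of 1496, and Section 6.3 is satisfied by fewer than either.

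The rule also counts the wrong thing. A contact is not an examination: the person may refuse, or may come and be found ineligible. The zero-case assurance is a statement about people examined, so a closing rule that counts contacts cannot show whether it was achieved. Under Section 6.3 as written, the study could close with well under 998 examined, and nothing in the plan would require the 5% to be restated.

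The base is loose as well. The percentage is taken over everyone enrolled in SOS, including the 18 + 5 = 23 subjects in whom SOS found lung cancer, who are outside the target population.

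**Working it through.** **Inputs.** SOS enrolment 1843, design rate 0.3%, zero-case limit 5%, 998, 50% drop-out and 1496 (all Section 6.1.1); contact threshold 80% (Section 6.3).

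**1. The plan's own figures.** Under the binomial model the chance of no case among n examined is 0.997^n. Setting this to 0.05 gives n = ln(0.05)/ln(0.997) = 997.08, rounded up to 998. This matches the plan.

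The total is reproduced by multiplying by 1.5: 997.08 × 1.5 = 1495.6, rounded up to 1496. Converting back, 1496/1.5 = 997, so the plan's factor corresponds to a loss of one third. A true 50% loss would need 998/0.5 = 1996, more than the 1843 who exist.

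**2. The closing threshold.** 0.80 × 1843 = 1474.4, so criterion 2 is met at 1475 contacts.
- Against the minimum: 1496 − 1475 = 21 (1.4% of 1496).
- Against Section 4: 1843 − 1475 = 368 people may remain uncontacted.

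**3. Uptake needed for 998 examinations.**
- From 1475 contacts: 998/1475 = 67.7%.
- From all 1843: 998/1843 = 54.2%.

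**4. Zero-case probability at a true rate of 0.3%.**

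| Contacted | Examined, plan's 1.5 factor | 0.997^n | Examined, true 50% loss | 0.997^n |
|---|---|---|---|---|
| 1475 (Section 6.3 floor) | 983 | 5.2% | about 737 | 10.9% |
| 1496 (Section 6.1.1 minimum) | 997 | 5.0% | 748 | 10.6% |
| 1843 (everyone, Section 4) | 1228 | 2.5% | about 921 | 6.3% |

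Reading the first two rows together isolates the effect of the 21-person gap: 0.2 percentage points on the plan's factor, 0.3 at a true 50% loss. Reading across the second row shows that the larger shortfall, 5.0% against 10.6%, is present even when the 1496 minimum is met exactly. It comes from the 1.5 multiplication in Section 6.1.1.

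**The case against.** The sponsor can fairly say that 80% is a floor. Section 4 plans to contact everyone, and Section 6.4 says that all patients defined by the inclusion criteria will be included. Closing at 1475 is therefore permitted, not planned. A reader might infer that a study closed under Section 6.3 cannot have reached 1496. The documents do not support that, since a study that contacts 1496 or all 1843 also satisfies the rule. Nor does contact alone end the study: the other two conditions must hold too, although neither sets a number of subjects.

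A reader might also attribute the rise from 5% to 10.9% to the closing rule. That is not supported either, because 1496 at 50% loss already gives 10.6%. Section 6.1.1 moreover gives 50% as an upper limit on drop-out, so 737 examined is a pessimistic case and not a forecast.

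It is tempting to add that deceased subjects help to fill the 80%. They do the reverse: they sit in the denominator and cannot themselves be contacted, so they make the threshold harder to reach. A bias from leaving hard-to-reach subjects out is plausible for mortality and for the count of cancers in the SOS cohort, but the documents give nothing from which to size it.

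Finally, the cohort is closed, so no closing rule can guarantee 998 examinations. That is true, and it limits what a fix can do. What stands after all this is that Section 6.3 allows fewer than Section 6.1.1 requires, allows fewer than Section 4 promises, and is not tied to completed examinations.

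**Conclusion.** The inconsistency is real. Its numerical part is small: 21 people, worth 0.2 to 0.3 percentage points of zero-case probability. The part that matters is the unit. The rule is silent on the number examined, which alone determines whether the 5% assurance holds. At the floor that assurance needs 67.7% of those contacted to be eligible and attend. At a true 50% loss even full contact leaves about 921 examined and a 6.3% zero-case probability, so correcting Section 6.3 does not by itself secure the 5%.

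This rests on taking 1843 as the base of the 80%, as the wording of Section 6.3 indicates, and on the plan's own zero-case model at 0.3%. It also treats the 1496 as a number of people before any loss, so that it can be compared with contacts. If it means people enrolled or eligible, the gap is wider.

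**What to change.** Replace criterion 2 of Section 6.3 with: all SOS subjects without confirmed lung cancer have been contacted, or recorded as deceased or untraceable after a fixed number of attempts. Add that the number with a completed DTS is reported against 998 and, if it is lower, that the achieved zero-case probability 0.997^n is stated in place of 5%.

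This brings Section 6.3 into line with Section 4 and the population in the Synopsis, and expresses the result in the unit on which the sample size rests. It does not guarantee 998 examinations, and some hard-to-reach subjects will still be missing, but they will be counted and visible.

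The cost is a short change of text and calls to at most 368 further subjects, whom Section 4 already undertakes to contact.

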6.4. Study duration

The start of the study is planned for September 2017. All patients defined by inclusion criteria will be included in the study. The enrollment is done by email. Patients are advised to contact the administrative staff to book an appointment to perform the exam. If the study is completed prematurely, the reasons must be documented. The last patient is expected to enter the study at the end of August 2018.

7. DTS evaluation and revision

Blinded independent central reviewing for DTS.

8. Independent data monitoring committee

This trial will NOT be monitored and scrutinized by an Independent Data Monitoring Committee (IDMC) because no toxicity is expected due to the DTS examination.

9. Quality of life evaluation

Although reducing mortality and morbidity still represent the crucial issue in clinical research, efforts to reduce adverse effects and control symptoms have reached a prominent role in devising therapeutic strategies.

Cancer treatments may produce adverse effects and diminish the QoL even when survival is extended. Progress in the acceptance of new cancer therapies is sometimes critically dependent on their QoL consequences.

Health-related QoL is a multidimensional concept which represents the physiological, psychological and social influences of the disease and the therapeutic process from the patient's perspective. It comprises four principal components: physical, emotional and social well-being, and daily-life functioning.

9.1. Rationale

In 'SOS trial', QoL is a secondary endpoint. Since no difference in QoL is expected due to physical events only emotional, social, and cognitive events will be analyzed.

9.2. QoL instrument

In order to understand the impact of long-term psychosocial outcomes of lung cancer screening a QoL questionnaire will be adopted to measures the effectiveness of a screening program of the smoking habits of the subjects, anxiety and decision satisfaction. The reliability and validity of the questionnaire are highly consistent across different language-cultural groups.

10. Cost-effectiveness analysis

During the study the costs associated with the DTS procedure are evaluated, comparing them to those incurred for the execution of the CT in the subjects positive to the DTS.

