Overall Study design	
The study aims to evaluate the lung cancer detection rate. Patients that previously were enrolled in SOS study will be called by project assistants and booked for DTS examination. In case the subject refuses to perform examination a phone interview for follow-up will be carried out acquiring information on the status of the subject, on the variation of quality of life, on smoke habits and on attitude toward lung cancer screening.
 
For the subject accepting the DTS examination the same questionnaire will be filled onsite just before examination. DTS will be then performed and blindly evaluated by two radiologists. DTS findings will be classified based on their dimension (large axis measurement), radiological characteristics (calcific, pleural, solid, partially solid and ground glass opacity) and position (in the 5 lobes). Findings will be then classified using LUNG-RADS [1]. The results of the DTS,in case of negative report, will be communicated with a letter to the patient.
 
The subjects with one or more nodules larger than 5 mm, not clearly benign, will undergo diagnostic contrast enhanced CT and will be followed according to Fleischner society [2] criteria.

	Discordant and positive cases will be discussed in a consensus session among radiologists and thoracic surgeons. The consensus results will be used in the following analysis.
Endpoints	
Primary
 
Lung cancer detection rate.
 
Secondary
 
 • Percentage of lung cancer addressed to radical surgery treatment; • Sensitivity of DTS evaluating the number of lung cancer occurred in the population of SOS study in the last 5 years; • Mortality • Overall survival (OS) • Quality of Life (QoL) • Cost-effectiveness
Eligibility criteria	
Inclusion criteria:
 
 • current or former smoker status; • for former smokers, the maximum time since quitting smoking must be below 10 years. • smoking history of at least 20 pack-years; • age 45-80 years; • no previous history of cancer in the 10 years before the beginning of the study; • be able to stand and hold the breath for 11 seconds during image acquisition • previous participation to SOS trial 
Exclusion criteria:
 
 • pregnancy

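### Section 9.2 sets out to measure the effectiveness of screening on smoking, anxiety and decision satisfaction, but there is no unscreened comparator, and the plan's three lists of questionnaire content disagree

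*Combined protocol and SAP*

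**What the plan says.** QoL is a secondary endpoint (synopsis, Endpoints; Section 9.1). Three places describe what will be collected.

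- Section 9.2 gives the purpose, "In order to understand the impact of long-term psychosocial outcomes of lung cancer screening", and then says that "a QoL questionnaire will be adopted to measures the effectiveness of a screening program of the smoking habits of the subjects". Satisfaction with the decision and anxiety are listed as well. The instrument is not named.
- Section 9.1 says that "only emotional, social, and cognitive events will be analyzed".
- The synopsis (Overall Study design) deals with both groups of subjects. For those who decline: "In case the subject refuses to perform examination a phone interview for follow-up will be carried out". It covers the subject's status and asks "on the variation of quality of life, on smoke habits and on attitude toward lung cancer screening". For those who accept: "For the subject accepting the DTS examination the same questionnaire will be filled onsite just before examination".

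Previous participation in SOS is an inclusion criterion (Section 3.1). Section 4 has subjects confirm, on arrival at the hospital, that they still meet the SOS criteria; Section 3.1 limits former smokers to less than 10 years since quitting. Section 6.2 (Analysis) contains Lung-RADS classification, ROC analysis and Krippendorff's alpha, and nothing on QoL or smoking.

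**The concern.** A claim about the effectiveness of a screening programme is a causal claim. It needs to be known, or credibly estimated, what smoking, anxiety and satisfaction would have been without screening. Here everyone was screened in SOS. Smoking can change over five years for many other reasons, and nothing in the plan separates those from screening. If the aim stays as worded, the report may be asked to answer a question that the data cannot answer.

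The second problem is one of definition. If the domains to be analysed and the content of the questionnaire differ, the QoL endpoint is not fixed in advance, and a reader cannot tell which scales will be reported.

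**Working it through.** The documents give no sample size, effect size or margin for QoL, so there is no planned figure to reproduce. The check compares the texts, with two short calculations.

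**1. Is there any group that could serve as a comparator?**

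- *Never-screened subjects:* none. Section 3.1 requires participation in SOS.
- *SOS subjects without the one-year DTS:* Section 6.1.1 gives 1843 enrolled and 1703 with the one-year DTS, so 1843 − 1703 = 140 without it. They belong to the cohort whose baseline findings are reported there, so they are not unscreened.
- *Subjects who decline the five-year DTS:* also screened in SOS, self-selected, and interviewed by phone rather than on site. Those who accept answer before their examination, so neither group has had the new DTS when it answers. The comparison would not isolate even this round.
- *External data:* Section 10.1.2 names two CT screening trials, but for the economic evaluation. None is named for QoL or smoking.

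No comparator remains.

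**2. How large could ordinary change be?** Assume a constant yearly quit rate q unrelated to screening and no relapse. The share of smokers who have quit by year 5 is 1 − (1 − q)^5.

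| q (assumed) | Quit by year 5 |
|---|---|
| 1% | 1 − 0.99^5 = 4.9% |
| 2% | 1 − 0.98^5 = 9.6% |
| 3% | 1 − 0.97^5 = 14.1% |
| 5% | 1 − 0.95^5 = 22.6% |

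The documents give no quit rate, so this is an illustration. Without a comparator, a smoking percentage at recall cannot be told apart from such a background.

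**3. Do the content lists agree?**

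| Content | 9.1 | 9.2 | Synopsis |
|---|---|---|---|
| Emotional | yes | through anxiety | not named separately |
| Social | yes | no scale named | not named separately |
| Cognitive | yes | no scale named | not named separately |
| Smoking | no | yes | yes |
| Decision satisfaction | no | yes | no |
| Attitude to screening | no | no | yes |
| Change in QoL | no | no | yes |

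Of the three domains in 9.1, one (emotional) has a matching item in 9.2. The synopsis speaks of change in QoL, but no SOS baseline for it is described.

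**4. Which smoking change can still be estimated?** The limit on time since quitting, re-checked at recall, could select on the outcome.

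- *Smokers at SOS entry.* Whoever quit afterwards has been abstinent for at most the gap between entry and recall. That is about 5 years (Section 2.1), or about 1 + 5 = 6 if the five years run from the one-year DTS (Section 6.1.1). It cannot exceed about 8.5 years, because the hospital has had DTS since March 2010 (synopsis, Background) and the last entry is planned for the end of August 2018 (Section 6.4). All are under 10, so nobody is lost for having quit.
- *Former smokers at SOS entry.* Someone who had quit 6 years before entry and stayed abstinent is at 6 + 5 = 11 years and no longer qualifies. Someone with the same history who relapsed is a current smoker and stays in. The re-check therefore selects on relapse.

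Quitting among entry smokers is the usable figure. Overall paired change, which mixes in relapse, is distorted.

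**The case against.** The best reply is that 9.2 is loosely worded and intends only to describe subjects about five years after SOS. It speaks of long-term psychosocial outcomes, and Section 6.2 plans no analysis that would present a percentage as an effect. QoL is secondary, and nothing in the primary endpoint or sample size depends on it. This largely stands. It limits the weight of the point and supports a change of wording, but the text still says effectiveness.

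Three stronger readings are tempting, and the documents do not support them.

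- *A reader might infer that the questionnaire misses the 9.1 domains and that two of the three will have no data.* Anxiety is an emotional measure, and the instrument is unnamed, so its scales cannot be inspected. What can be said is that social and cognitive coverage is not shown.
- *A reader might infer that giving the form before the DTS defeats its purpose.* It does mean that the effect of the present result is not seen, and no later assessment is defined: the appended EORTC leaflet refers to assessments set by the protocol, which sets none. But no section aims to measure the effect of this round's result. For a long-term description, answering before the new result is reasonable.
- *A reader might infer that ordinary quitting will be reported as a screening effect.* That is a prediction. It rests on assumed quit rates and on one ungrammatical sentence.

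A practical objection also stands. Paired change needs a link to SOS records. Section 15 says that data are collected anonymously and Section 18.2 assigns a serial number; neither describes a link to SOS identifiers.

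**Conclusion.** The concern holds in this form. The design cannot estimate an effect of screening on smoking, anxiety or decision satisfaction, because every subject was screened in SOS, no comparator is planned, and those who decline the DTS are not a valid control. The lists in 9.1, 9.2 and the synopsis disagree, so coverage of the social and cognitive domains is not shown. Neither the timing of the form nor the content of an unseen questionnaire is shown to be a defect.

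No bias in a planned estimate can be sized, because no QoL or smoking estimate is planned. The range of 4.9% to 22.6% shows only how much background quitting could occur under assumed rates of 1% to 5% a year without relapse. The conclusion on comparators does not depend on it. The point deserves correction because it changes what the trial may claim on a secondary endpoint; the primary endpoint is untouched.

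**What to change.** 1. In 9.2, replace the aim of measuring effectiveness with a description of smoking, anxiety and decision satisfaction about five years after SOS screening.
2. In 6.2, add for smoking the within-subject change from status at SOS entry to recall, with a 95% CI, reported as change and not as an effect of screening. Take the proportion who quit among entry smokers as the main figure. If relapse among entry former smokers is shown, say that the re-checked 10-year limit selects on it.
3. Show phone and on-site answers separately. The mode differs, and the eligibility re-check is described only for those who come to the hospital.
4. Name the questionnaire and make the lists in 9.1, 9.2 and the synopsis equal to the scales it contains. Keep change in QoL only if a baseline for it exists.

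The cost is edits to these sections, one merge with SOS entry data and a weaker claim. No new visit or group is needed. Before step 2 is adopted, confirm that SOS smoking status is on record and can be linked under Sections 15 and 18.2. If it cannot, drop step 2; the descriptive wording, separate reporting and aligned lists still apply.

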Background and rationale	
Lung cancer is the leading cause of cancer-related death around the world. In 2008 there were nearly 1.6 million new cases worldwide, accounting for the 12.7% of all new cancer diagnoses[4]. Despite decreasing trends in smoking and resulting decrease in lung cancer mortality, the population at risk for lung cancer continues to be large[5]. In the past years several programs have been developed to screen for lung cancer using low-dose chest computed radiography (CT). However, only recently different studies demonstrated a clear reduction in mortality[5,6]. In particular, NLST low dose CT screening trial demonstrated a 6.7% reduction in the death rate compared to chest X-ray with a positive screening test rate for lung cancer detection of 24.2%, compared to 6.9% for conventional X-ray[7]. The use of CT as a screening test has nonetheless recently prevailed over the concern for the cost and the radiation burden[8]. Digital tomosynthesis (DTS) is a limited angle tomography that allows reconstruction of multiple image planes from a set of projection data acquired over a relatively small angle of X-ray tube movement[9]. Santa Croce and Carle Hospital has this technology from March 2010, thanks to a donation of Fondazione CRC. Although it does not have the spatial depth resolution of computed tomography, it provides high-resolution images in the sagittal planes at a lower dose and cost than CT[10]. Several studies have shown that DTS offers advantages over conventional chest X-ray and comparable of those of CT[11–13]. The Studio OSservazionale (SOS) was a clinical trial conducted within Santa Croce e Carle Hospital sponsored by Fondazione CRC analysing smokers and former smokers aged 45–80 with no cancer diagnosis. All the subjects in whom a suspicious nodule was detected by DTS underwent diagnostic CT. The SOS study demonstrated that baseline DTS detected pulmonary abnormalities in 14.5% and lung cancer in 1.0% of the subjects[14], comparable to results obtained in CT screening programs. A second DTS, within the same study, executed one year later reported pulmonary abnormalities in 0.7% and lung cancer in 0.3% of the subjects[15].

1. Background and introduction

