10.1. Methods

10.1.1. Type of Economic Evaluation.

Since a predictable variance in effectiveness, a cost-effectiveness analysis is justified.

10.1.2. Choice of Comparator.

The results are compared to the data obtained from the NELSON study and the National Screen Screening Trial for the evaluation of the effectiveness of screening in the control of 10-year mortality due to lung cancer.

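### The planned cost comparison sets DTS against the CTs that DTS itself triggers, so it does not show whether DTS screening is cost-effective and can give the wrong sign

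*Combined protocol and SAP*

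**What the plan says.** Cost-effectiveness is a secondary endpoint in the Synopsis and is listed again in Section 2.2. The opening paragraph of Section 10 says that DTS procedure costs will be evaluated, "comparing them to those incurred for the execution of the CT in the subjects positive to the DTS". Section 10.1.1 adds that "a cost-effectiveness analysis is justified". Section 10.1.2, on the choice of comparator, names two external screening trials, but only for effectiveness against 10-year lung cancer mortality.

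Section 4 explains how a CT arises in this study: "The subjects with one or more nodules larger than 5 mm, not clearly benign, will undergo diagnostic contrast enhanced CT". The Synopsis describes the same rule for the earlier study: "All the subjects in whom a suspicious nodule was detected by DTS underwent diagnostic CT".

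The Synopsis background presents DTS as available "at a lower dose and cost than CT". No section gives a unit cost, adds the work-up CTs to the cost of DTS, costs an alternative strategy or defines a cost-effectiveness ratio.

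**The concern.** A CT in a DTS-positive subject takes place because DTS was done first. In an economic evaluation it belongs on the DTS side of the ledger, next to the DTS examination. Section 10 places it on the opposite side, so two components of one strategy are compared and no alternative strategy is costed.

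Lower cost is part of the protocol's argument for DTS, so readers will take the economic result as a test of that argument. If totals are compared, the result also moves in the wrong direction. Fewer positives shrink the CT total and make DTS look relatively dearer, although the DTS pathway has become cheaper.

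Section 10.1.2 does not repair this. Effects would be set against external screening trials and costs against the study's own work-up CTs, and no coherent incremental ratio can be formed from those two pieces.

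**Working it through.** The plan states no cost, saving or ratio, so there is no figure to reproduce. The check is a break-even calculation.

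**Inputs**
- p, the share of DTS subjects sent to CT. The Synopsis background gives two SOS rates: "baseline DTS detected pulmonary abnormalities in 14.5% and lung cancer in 1.0% of the subjects", and a second DTS "executed one year later reported pulmonary abnormalities in 0.7% and lung cancer in 0.3% of the subjects". So p = 0.145 or 0.007. These are abnormality rates and stand in for CT referral.
- r, the unit cost of DTS divided by that of CT. It is not given. The background implies r < 1, so the range 0 to 1 is examined.
- N = 1496, the minimum sample in Section 6.1.1. It only sets the scale.
- Simplifications: imaging costs only, one CT price, no work-up after CT.

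**Step 1. Section 10 read as a comparison of totals.** In units of one CT, DTS costs N·r and CT in positives costs N·p. DTS looks cheaper only if r < p, that is r < 0.145 or r < 0.007. As a CT/DTS price ratio this is above 1/0.145 = 6.9 or 1/0.007 = 143.

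**Step 2. Whole pathways.** DTS plus CT in positives costs N·(r + p), and CT for everyone costs N. DTS is cheaper if r < 1 − p, that is r < 0.855 or r < 0.993 (CT/DTS above 1/0.855 = 1.17 or 1/0.993 = 1.007).

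**Step 3. Where the two disagree.** The sign is reversed for p < r < 1 − p.

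| p | r with reversed sign | width, 1 − 2p |
|---|---|---|
| 0.7% | 0.007 to 0.993 | 0.986 |
| 5% (assumed) | 0.05 to 0.95 | 0.90 |
| 14.5% | 0.145 to 0.855 | 0.71 |
| 20% (assumed) | 0.20 to 0.80 | 0.60 |
| 30% (assumed) | 0.30 to 0.70 | 0.40 |

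Example with p = 14.5% and r assumed to be 0.5: DTS costs 1496 × 0.5 = 748 and CT in positives 1496 × 0.145 = 217, so DTS looks dearer. The pathway costs 748 + 217 = 965 against 1496, so it is cheaper by 531.

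Outside the interval the two agree. At r = 0.1 DTS is cheaper both ways (149.6 v 216.9; 366.5 v 1496). At r = 0.9 it is dearer both ways (1346.4 v 216.9; 1563.3 v 1496).

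**Step 4. Section 10 read as a comparison per examination.** The comparison is r against 1, so DTS looks cheaper for every r < 1. This is wrong only for 1 − p < r < 1: 0.855 to 1 at p = 14.5%, and 0.993 to 1 at p = 0.7%.

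**Step 5. Dependence on a single CT price.** Work-up CT here is contrast-enhanced, whereas the CT screening described in the background is low-dose, with a quoted positive rate of 24.2%. As an illustration, assume contrast CT = 1, low-dose CT = 0.5, DTS = 0.4 and p = 14.5%. The DTS pathway costs 0.4 + 0.145 = 0.545 per subject.
- Against CT for all at the contrast price: 0.545 v 1, DTS cheaper.
- Against low-dose CT without work-up: 0.545 v 0.5, DTS dearer.
- Against low-dose CT with work-up: 0.545 v 0.5 + 0.242 = 0.742, DTS cheaper.

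The limits in Steps 2 to 4 therefore hold only under the single-price simplification.

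**The case against.** The strongest reply is that Section 10 means cost per examination. In a single-arm study only DTS-positive subjects have a CT, so naming them may simply say where CT costs can be observed. The wording allows this. If it is what is meant, the range of wrong signs is narrow, and the remark about fewer positives making DTS look worse no longer applies. It does not make the analysis adequate, however. Work-up CT is then missing from the DTS cost altogether, no cost is related to an effect, and the result adds little to the background's own premise that DTS costs less than CT.

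A second reply is that a comparator is already named in Section 10.1.2. It is, but for effectiveness only.

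A reader might infer that the plan is bound to give a wrong answer on whether DTS saves money. The documents do not support that. They give no unit costs, they never pose the question as one of saving money, and the sign depends on r, on p and on which reading is meant.

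**Conclusion.** The point holds in a conditional form. As written, Section 10 does not show whether DTS screening is cost-effective, because CTs that follow from DTS are treated as its comparator, and the result can have the wrong sign. On the totals reading the reversal covers 71% of the range of r from 0 to 1 at p = 14.5%, and about 99% at p = 0.7%. On the per-examination reading it covers 14.5% and 0.7% of that range.

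These sizes rest on imaging costs only, on one CT price and on SOS abnormality rates standing in for CT referral. Referral in this study has its own size and appearance criteria, and the five-year rate is unknown. Cost-effectiveness is a secondary endpoint and the detection-rate result does not depend on it, so this should be corrected but does not threaten the primary analysis.

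**What to change.** Rewrite the opening of Section 10 as follows.

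1. Define the cost of the DTS strategy as DTS in all subjects plus diagnostic CT in DTS-positives. Report cost per subject screened and cost per histologically proven cancer detected.
2. As a modelled scenario, compare this with low-dose CT in all subjects plus diagnostic CT work-up of its positives. Use separate unit costs for low-dose and contrast-enhanced CT. Vary the CT positive rate (24.2% from the Synopsis background as one input) and the cancer yield over stated ranges.
3. State in Section 10.1.2 that the two external trials inform effectiveness, and name the modelled strategy as the cost comparator.

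No new procedure in subjects is needed. The work is a rewritten paragraph, a spreadsheet model and the collection of unit costs, for which the plan names no source and the Section 22.2.4 checklist has no form. The main limitation is that the CT-strategy inputs have to be assumed, because DTS-negative subjects receive no CT.
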